(S)AE	(Serious) Adverse Event
PIT	Palvovian to instrumental transfer
SPC	Summary of Product Characteristics; in Dutch: officiële productinformatie IB1-tekst
Sponsor	The sponsor is the party that commissions the organisation or performance of the research, for example a pharmaceutical company, academic hospital, scientific organisation or investigator. A party that provides funding for a study but does not commission it is not regarded as the sponsor, but referred to as a subsidising party.
SUSAR	Suspected Unexpected Serious Adverse Reaction
UAVG	Dutch Act on Implementation of the General Data Protection Regulation; in Dutch: Uitvoeringswet AVG
WMO	Medical Research Involving Human Subjects Act; in Dutch: Wet Medisch-wetenschappelijk Onderzoek met Mensen

SUMMARY

Rationale: Intranasal esketamine is a new antidepressant drug with an alternative mechanism of action than routinely used antidepressants. Experience with esketamine especially in more severely treatment resistant depressed (TRD) patients is limited and should be quantified more in terms of effectiveness and acceptability.

Objective: (1) To collect pseudo-anonymised short- and long-term effectiveness and acceptability data for the treatment with esketamine intranasal in TRD-patients treated in collaborating esketamine treatment centres in the Netherlands. (2) To pool pseudoanonymised data of effectiveness and acceptability of esketamine intranasal based on clinical registrations in patient's real-world health records. (3) To use predicted treatment response based on pooled clinical and behavioural data as pre-selection tool.

Study design: unblinded cohort study of patients who are treated with intranasal esketamine (open label). For the objectives of this study, no other routines will be applied apart from the necessary measurements in clinical medical records of the patients, who will provide informed consent for the data-collection.

Study population: Patients with treatment resistant depression (TRD; defined as non-responsive to ≥ 2 antidepressant trials used at adequate dosages for ≥ 6 weeks), aged ≥ 18 years, clinically eligible for treatment with esketamine nasal spray

Intervention: Open-label esketamine intranasal spray at 28-84mg/session twice weekly for 4 weeks (as addition to an antidepressant). Treatment responders will enter a Continuation (maintenance) Phase with 4 weeks weekly and thereafter -if possible- lower frequency of administration.

Main study parameters/endpoints: Primary outcome: change in MADRS-score relative to baseline. Secondary outcomes: change in IDS-SR-score relative to baseline; Quality of life and Daily functioning, adverse effects (KSET), cost-effectiveness, treatment discontinuations and behaviour on the Pavlovian instrumental transfer (PIT) task.

Nature and extent of the burden and risks associated with participation, benefit and group relatedness: as a potential alternative treatment for TRD, patients might benefit from this treatment. As long as the manufacturer's precautions and instructions are followed there is a minimal risk involved in this treatment. In this project no additional interventions or extra measurements will be performed apart from clinically relevant assessments for routine health care, except for the PIT task. We therefore request for a non-WMO statement.

INTRODUCTION AND RATIONALE

Treating Major Depressive Disorder (MDD) is a health care challenge of paramount importance worldwide, as the disease is the leading cause of disability worldwide, impairs overall health, social functioning, productivity and reducing life expectancy with 10 years (Walker 2015; Sobocki 2006; Mathers 2006). About one-third of patients with MDD fail to achieve remission despite treatment with multiple antidepressants, hence have treatment-resistant depression (TRD) (Fava 2003). In patients who respond, time to onset of effect is typically 3 to 7 weeks, during which time patients remain symptomatic and at risk of self-harm (Rush 2006). There is an unmet need to develop novel treatment providing an effective, rapid-acting and sustained relief of depressive symptoms.

Research on mood disorder pathophysiology has implicated abnormalities in glutamatergic transmission (Sanacora 2012; Duman 2019). Ketamine is a noncompetitive antagonist of glutamate receptors of the N-methyl-D-aspartate (NMDA) type, which can make fast excitatory glutamate transmission happen, increase the release of brain-derived neurotrophic factor and stimulate synaptogenesis, with mood-elevating effects occurring as rapid as within several hours (Kavalali 2012). Esketamine, the s-enantiomer of ketamine, which has a higher affinity for the NMDA receptor than the r-enantiomer, has recently been approved in the United States as a nasal spray for treatment resistant depression (TRD). The efficacy and safety of esketamine for TRD were evaluated in three 4-week, placebo controlled, parallel-group studies with (two studies including adults 18 to 65 years of age (total of 197+297=494 patients), and one in patients of 65 years and above (n=138)) and one longer-term randomized withdrawal study. The long-term safety was evaluated in a 12-months open-label safety study. In summary, Phase II and III studies with esketamine in n=632 patients, demonstrated rapid onset and persistent efficacy of intranasal esketamine administered adjunctive to an ineffective oral antidepressant, compared to placebo nasal spray in patients with TRD (Singh 2016; Daly 2018; Popova 2019; Fedgchin 2019). In addition, there is evidence of sustained benefit over a variable time with a maximum of 92 weeks in a phase III long-term maintenance study (Daly 2019). Despite this evidence, relatively few studies have been performed on esketamine, and even less in “real world” TRD patients with chronic and often more severely treatment resistant depression. Moreover, the patient characteristics of those who respond versus those who remain symptomatic after treatment with intranasal esketamine remain unclear.

Since December 18th 2019, esketamine intranasal obtained a European marketing authorization from EMEA. Thereafter, the manufacturer issued a compassionate use program (CUP) for the Netherlands before the reimbursement would be established, aiming at severely treatment resistant depressed patients (e.g. unsuccessful response to MAO-Inhibitors and/or ECT). As treatment with esketamine intranasal requires protocolized administration under strict supervision of patients in at least a day-care treatment facility, a limited number of centres will provide esketamine treatment, initially via the CUP, which, after reimbursement, was continued with new treatment centres. Current centres where esketamine intranasal spray treatments are administered: Radboudumc, Amsterdam UMC, UMC Utrecht, LUMC, GGZ Drenthe, ApareeGGZ, UMCG, Elisabeth Tweesteden Ziekenhuis, Maxima Medisch Centrum Eindhoven, Mondriaan / PsyQ Maastricht, GGZ Delfland, Antonius

ziekenhuis Nieuwegein, Parnassia Psy-Q Den Haag, Parnassia Antes, Parnassia Noord-Holland Castricum, Synaeda/GGZ Friesland, Vincent van Gogh, ProPersona, GGNet, GGZ Centraal, Reinier v Arkel, Amphia, Emergis, Rivierduinen, GGZ Noord-Holland Noord, Lentis, Spaarne gasthuis, Altrecht, Isala, Rivierenland, Ziekenhuis Groep Twente, Gelre Ziekenhuis, GGZ InGeest. These centres are collaborating on exchanging treatment protocols and clinical experience in order to increase the knowledge with this new application.

OBJECTIVES

Primary Objective: To collect pseudo-anonymized short- and long-term effectiveness and acceptability data for the treatment with esketamine intranasal in treatment resistant depressed patients treated in collaborating esketamine treatment centres in the Netherlands.

Secondary Objective(s):

[figure not shown]
To pool pseudoanonymised data of effectiveness and acceptability of esketamine intranasal from based on clinical registrations in patient's real-world health records.

To use predicted treatment response based on pooled clinical and behavioural data as pre-selection tool.

1. STUDY DESIGN

This is an unblinded cohort study of patients who are treated with intranasal esketamine (open label). This cohort is a cohort study of real world regular treatment with esketamine intranasal administration. For the objectives of this study, no other routines or interventions will be applied apart from the necessary measurements used for optimal clinical care and decisions about effectiveness and acceptability, except for the PIT task. All data, except for the PIT task, can be obtained from the clinical medical records of the patients, who will provide informed consent for the data-collection as described in this protocol. Data from the PIT task will be collected via online testing using Gorilla (cf. 'Online testing' covered under CMO2014/288).

Figure 1.

2. STUDY POPULATION

2.1 Population (base)

Depressed patients with TRD, referred to the hospital for treatment of their MDD.

2.2 Inclusion criteria

In order to be eligible to participate in this study, a subject must meet all of the following criteria:

- Clinical diagnosis of primary MDD, preferably confirmed by a structured clinical interview (MINI/SCID-I)
- Treatment Resistant Depression, defined as non-response to at least two antidepressants used at adequate dosages for a minimum of 6 weeks
- Age >18 years old (no maximum age)
- Current use of (and compliance to) an antidepressant (non-SSRI/SNRI is allowed)

2.3 Exclusion criteria

A potential subject who meets any of the following criteria will be excluded from participation in this study:

- Current psychotic illness
- Bipolar disorder
- Severe suicidal/homicidal risk (to be determined by psychiatrist)
- Insufficient understanding of Dutch to fill-out questionnaires and/or understand information
- Unable to self-administer esketamine nasal spray
- History of moderate-severe substance abuse or dependence meeting DSM-5 criteria
- Pregnancy or wish to become pregnant
- No form of adequate anti-conception (both genders)
- Instable epileptic disease/seizures in previous 6 months
- Unstable hypertension (>140/90 mmHg) or recent cardiovascular event (cerebrovascular, myocardial, aneurysmal vascular disease, angina-pectoris, . hemodynamically significant valvular heart disease, NYHA Class III-IV heart failure)
- Hypo-thyroidism, liver-failure/cirrhosis
- Any anatomical or medical condition that may impede delivery or absorption of intranasal esketamine
- Other unstable somatic/medical illness

- Previous non-response to esketamine (intranasal) or ketamine in current MDD episode
- Known allergies, hypersensitivity, intolerance, or contraindications to esketamine/ketamine and/or its excipients

2.4 Sample size calculation

As this is a cohort study, in which we want to use clinical data for summary purposes regarding effectiveness and acceptability, we did not perform an a priori power calculation.

3. TREATMENT OF SUBJECTS

Although this is a non-interventional cohort study of routine medical treatment, we will here describe the esketamine intranasal treatment schedule.

3.1 Investigational product/treatment

Treatment will be provided according to the 'TREATMENT GUIDELINES for Esketamine Nasal Spray for the use of treating Physicians' as provided by the manufacturer.

In brief, treatment will be provided initially twice per week during the Induction Phase, followed by a Continuation (maintenance) Phase, where in week 5-8 treatment will be provided once weekly and from week 9 onwards dosing can be tried to be reduced to once every two weeks (Figure 1). Usual initial dosages are 56mg/session, which may be increased to 84mg/session. Especially in elderly the initial starting dose will be lower (28mg/session), and if responsive, patients may stay on that dosage. Dosing frequency will be individualized to the lowest frequency to maintain remission/response. At the end of Induction Phase, evidence of therapeutic benefit (based on the clinician's evaluation of symptomatic change and/or improvement in functioning or quality of life) will be evaluated to determine need for continued treatment in the Continuation (maintenance) Phase. After depressive symptoms improve, treatment is recommended for at least 6 months.

Each treatment session consists of administration of esketamine nasal spray and post-administration observation under the supervision of a healthcare professional. Patients will administer the nasal spray themselves. Because of possible nausea and vomiting after administration of esketamine nasal spray, patients should not eat for at least 2 hours before administration and not to drink liquids at least 30 minutes prior to administration. Patients who require a nasal corticosteroid or nasal decongestant on a dosing day should be advised not to administer these medications within 1 hour before administration of esketamine nasal spray.

All patients remain at the clinical site until safety procedures have been completed (monitoring of blood pressure and dissociative symptoms) and the patient is ready for discharge. Readiness to leave is assessed based on clinical judgement of dissociative symptoms measured 40 minutes after the last dose administered or as soon as possible after the patient wakes up. Patients must not drive a car or work with machines for 24 hours after esketamine dosing, therefore patients need to have transportation home after the procedure.

3.2 Use of co-intervention (if applicable)

Patients will continue their antidepressant medication (SSRI, SNRI, TCA), which might be optimized according to dosage or therapeutic drug monitoring (if appropriate).

If possible, a maximum of 3 mg lorazepam (or equivalents) daily is used, and preferably stopped during the treatment.

3.3 Escape medication (if applicable)

N/A; this is left to the judgement of the clinician

4. INVESTIGATIONAL PRODUCT

4.1 Name and description of investigational product(s)

Esketamine intranasal (Spravato).

4.2 Summary of findings from non-clinical studies

See SPC of Spravato 28mg nasal spray at

<https://www.medicines.org.uk/emc/product/10977/smpc#gref>

4.3 Summary of findings from clinical studies

See SPC of Spravato 28mg nasal spray at

<https://www.medicines.org.uk/emc/product/10977/smpc#gref>

4.4 Summary of known and potential risks and benefits

See SPC of Spravato 28mg nasal spray at

<https://www.medicines.org.uk/emc/product/10977/smpc#gref>

4.5 Description and justification of route of administration and dosage

Nasal spray administration of esketamine has approximately 50% bioavailability compared to i.v. administration, while oral administration reduces bioavailability to approximately 8-18.6% (Andrade 2015; 2017; Janssen 2019; Perez-Ruixio 2020).

4.6 Dosages, dosage modifications and method of administration

Esketamine treatment will be provided via nasal spray. Each device contains 28 mg of esketamine, which is 2 sprays, one for each nostril. It is intended for administration by the patient under the supervision of a healthcare professional. In elderly (age ≥ 65 years) the starting dose will be 28 mg, in younger adults the starting dose will be 56 mg (2 devices). If adverse effects are tolerable, the next session the dose will be increased to a maximum of 84 mg/session (i.e. 3 devices). To prevent loss of medication, the device should not be primed before use.

4.7 Preparation and labelling of Investigational Medicinal Product

The product will be obtained from Janssen Inc. either via the CUP or after reimbursement is established via the hospital pharmacy. Labelling will be done according to GMP.

4.8 Drug accountability

N/A Routine delivery of drug via pharmacy.

5. NON-INVESTIGATIONAL PRODUCT

N/A

6. METHODS

6.1 Study parameters/endpoints

6.1.1 Main study parameter/endpoint

Primary endpoint is the change (relative to baseline) in clinician-rated MADRS score (Montgomery 1979) at 4 and 8 weeks.

6.1.2 Secondary study parameters/endpoints

Secondary endpoints are:

- The change (relative to baseline) in clinician-rated MADRS score (Montgomery 1979) over time measured in 4 weeks intervals after week 8.
- The change (relative to baseline) in self-rated IDS-SR score (Rush 1996; Trivedi 2004) at 4 weeks and over time measured in 4 week intervals thereafter.
- Quality of Life measurement (EQ-5D-5L; Janssen 2013) at 4 weeks and over time measured in 4 week intervals thereafter (relative to baseline)
- Level of functioning at 4 weeks (WHODAS-2.0; Forero 2018) and over time measured in 4 week intervals thereafter (relative to baseline)
- Cost-effectiveness (modified TiC-P) at 4 and 8 weeks and 3 monthly intervals thereafter (relative to baseline)
- The change in mood (before-after) esketamine intranasal spray per session as measured by a visual analogue scale before administration and after completion of the session (before leaving).
- Occurrence of adverse effects including dissociative symptoms at T=40 min after administration (or as close as possible) and at the end of the session as measured with the KSET (Short 2020) per session
- Discontinuation rates: due to adverse effects of the treatment or other reasons.
- Changes in blood-pressure during esketamine intranasal sessions (baseline, 10, 40, 90 minutes)
- Follow-up 3 months after discontinuation of intranasal esketamine treatment.

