6.4.1 Specific criteria for withdrawal

- Intolerance of esketamine intranasal treatment
- Non-response to the treatment after 4 weeks

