8.2 Secondary study parameter(s)

For secondary outcome study parameters (IDS-SR, QoL and level of functioning) we will use a comparable approach as for the primary study outcome.

Discontinuation rates will be described over time, also in relation with level of TRD.

Occurrence of dissociative symptoms and blood-pressure per session will be examined for stability over time. Moreover, the severity of these adverse effects and the variation thereof between patients will be described descriptively.

For the second aim of the project, we aim to pool this data across different treatment centres in order to increase power and obtain more quantitative information about possible characteristics of responders vs non-responders.

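### The discontinuation endpoint separates only adverse effects from other reasons, so the overall and residual rates, and their relation with TRD level, cannot be read as acceptability

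*Protocol*

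**What the plan says.** The primary objective is "To collect pseudo-anonymized short- and long-term effectiveness and acceptability data for the treatment with esketamine intranasal", so acceptability in the short and long term is part of what the cohort is for. Section 10.6 adds that the planned publication will explore effectiveness and acceptability against the level of TRD at the start of treatment.

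For discontinuation, Protocol section 6.1.2 defines the endpoint as "Discontinuation rates: due to adverse effects of the treatment or other reasons". The analysis in section 8.2 is one sentence: "Discontinuation rates will be described over time, also in relation with level of TRD".

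Elsewhere the protocol foresees stops of different kinds:

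- Section 6.4.1 lists two criteria side by side: "Intolerance of esketamine intranasal treatment" and "Non-response to the treatment after 4 weeks".
- Section 3.1 says that therapeutic benefit at the end of induction "will be evaluated to determine need for continued treatment in the Continuation (maintenance) Phase".
- Section 3.1 also states: "After depressive symptoms improve, treatment is recommended for at least 6 months". That is a minimum length, so improved patients may stop at some later time.

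Section 6.1.2 also lists follow-up 3 months after discontinuation as a secondary endpoint, whereas section 6.6, on follow-up of subjects withdrawn from treatment, is marked not applicable.

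**The concern.** The endpoint is coarser than the protocol's own list of withdrawal criteria. It keeps intolerance as a category but places non-response in a residual group. Any later loss of response and any stop after sustained improvement go there too. These have opposite meanings. A higher rate of the first two is bad news about the treatment, and a higher rate of the third is not. A rate that rises with both failure and success has no direction.

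The relation with TRD is exposed in the same way. More resistant patients may stop more often because treatment failed, and less resistant patients more often because it worked. The two patterns can offset each other in a combined rate.

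The definition also governs what is collected. Data are abstracted from routine health records (sections 1 and 10.1) at more than 30 listed centres. If centres code two categories only, a later analysis plan cannot restore the reasons without going back to the records.

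**Working it through.** **No figure to reproduce.** The protocol states no discontinuation rate, and section 2.4 states that no power calculation was done. What follows is an illustration on assumed rates. N = 350 is borrowed from the prediction-model sample in section 8.3 and is not a target for this endpoint.

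**1. How much the two-way split leaves open.** Let *a* be the proportion stopping for adverse effects, *o* the proportion stopping for other reasons, and *s* the share of *o* that is lack or loss of effect. The plan reports *a* and *o* but not *s*.

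- Failure stops = N × *o* × *s*
- Unfavourable stops = *a* + *o* × *s*

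| *a* | *o* | Other stops reported | *s* | Failure stops | Unfavourable stops |
|---|---|---|---|---|---|
| 10% | 50% | 350 × 0.50 = 175 | 20% | 35 | 10 + 10 = 20% |
| 10% | 50% | 175 | 50% | about 88 | 10 + 25 = 35% |
| 10% | 50% | 175 | 80% | 140 | 10 + 40 = 50% |
| 10% | 30% | 350 × 0.30 = 105 | 20% to 80% | 21 to 84 | 16% to 34% |
| 5% | 60% | 350 × 0.60 = 210 | 20% to 80% | 42 to 168 | 17% to 53% |

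Within each assumed pair of *a* and *o* the reported result is identical, while the unfavourable rate changes two- to threefold. The adverse-effect rate *a* is the same throughout, so that part of the endpoint is intact.

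**2. Relation with TRD: an assumed worst case.** Ignore neutral reasons and write the residual rate as failure stops plus stops after benefit.

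- Low TRD: 30 + 35 = 65%
- High TRD: 55 + 10 = 65%
- Ratio of failure stops: 55 / 30 = 1.83

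The combined rate shows no difference, although failure stops are 1.8 times as frequent in high TRD. The rates were chosen to cancel, and the tie appears only if everything is reduced to a single proportion at the end of follow-up.

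**3. What the time axis recovers.** Section 8.2 describes rates over time. If every failure stop in step 2 were non-response at week 4, the curves would stand near 30% and 55% soon after week 4 and meet only later. The time axis therefore separates early non-response from stops after benefit. It does not separate later loss of response from planned ends, because both occur during continuation. The unresolved mixing lies mainly there.

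**4. Whether symptom scores can stand in for the reason.** Only in part. Section 3.1 lets the clinician judge benefit on functioning or quality of life as well as symptoms, section 6.4.1 gives no response threshold, and section 6.3 lets MADRS and IDS-SR assessments thin out to every two months at the lower dosing frequencies. The last score before a late stop may be old and need not match the reason.

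**The case against.** The strongest reply is that pooling is inferred. The wording speaks of reasons in the plural and does not say they will go unrecorded or be reported as one rate. Section 8.3 promises a pre-registered analysis plan for each analysis, and competing-risk methods or sub-codes commonly belong in such a plan. The source record may hold the reason. Loss of response as a ground for stopping is stated nowhere, and a planned end after benefit is inferred from a minimum duration. The protocol never says that completing a beneficial course counts as discontinuation. Finally, this is one descriptive secondary endpoint.

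Much of this is fair, and it limits the point. It does not remove it. Nothing in the protocol requires the finer reasons to be recorded, and a later plan can analyse only what the centres captured. Whether a completed course counts as discontinuation is itself left open by the definition, which is a further reason to settle it there.

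A reader might infer that the long-term acceptability objective cannot be answered at all. The documents do not support that. Adverse-effect stops are a separate category, KSET and blood pressure are recorded per session and examined for stability over time, and repeated MADRS and IDS-SR scores could classify many stops. A reader might also infer that the link between discontinuation and TRD would vanish. That rests on rates chosen to cancel and on ignoring the time axis. Nor does the protocol state that the 3-month follow-up will be analysed as one undivided group. It states no analysis for that item.

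**Conclusion.** The point holds in a limited form. Followed as written, the residual category combines stops for lack or loss of effect with stops after sustained benefit. The overall and residual discontinuation rates, and their relation with level of TRD, then cannot be interpreted as acceptability. The problem is greatest during continuation, where loss of response and planned ends overlap in time. Discontinuation for adverse effects and per-session tolerability remain interpretable.

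On the assumed rates, one and the same report is compatible with unfavourable stopping of 20% to 50% (16% to 34% and 17% to 53% under the two other sets). These ranges show how far interpretation is left open and are not forecasts. The 65% against 65% example is an assumed worst case for a single end-of-follow-up proportion. The conclusion assumes that stops after improvement are counted as discontinuations and that centres code only the two named categories. The protocol excludes neither.

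Separately, the 3-month follow-up in section 6.1.2 and the not-applicable entry in section 6.6 do not agree and must be reconciled.

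**What to change.** In section 6.1.2, replace the two categories with a short list recorded at the stop in all centres:

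- adverse effect;
- non-response at the end of induction;
- later loss of response;
- planned end after sustained improvement;
- patient, logistic or reimbursement reason.

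In section 8.2, report cumulative incidence per reason with the other reasons as competing events, relate each reason to the DM-TRD score, and state that planned ends after benefit are not counted as poor acceptability.

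Report the 3-month follow-up by response status at the stop, and reconcile it with section 6.6.

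The cost is one coded field taken from the treating clinician's note and a competing-risk table in place of a simple rate. Some reasons will be judged imperfectly from records. Care does not change, and no stopping rule is proposed.
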